9.0 EVALUATIONS DURING AND AFTER TREATMENT

9.1 During Radiation Therapy

1. All patients will be evaluated by a radiation oncologist weekly during RT or more frequently as indicated.
2. An interim history and directed physical examination will be performed during the weekly treatment check with documentation of treatment-related acute toxicity
3. A CBC will be obtained during the course of radiation treatment.

9.2 Criteria for Going off Protocol

1. Non compliance with protocol requirements.
2. Patient request or withdrawal of consent.

9.3 Follow-up

Patients will be encouraged to return every 6 months for the first two years to Radiation Oncology and annually thereafter for follow-up. The medical oncologist will also evaluate the patient routinely per standard evaluation practices. This usually involves a CT or PET/CT every 6 months for 2 years following the completion of radiation treatment. All follow-up examinations, including laboratory work and imaging studies will be performed at the discretion of the treating physicians. However, if a patient relapses, either CT or PET imaging is highly recommended to ascertain sites of disease recurrence in relation to the radiation treatment fields.

9.4 Adverse Event Capture

Adverse event information will be collected for up to five years following completion of study treatment. Only adverse events that are related, probably related, or possibly related to study treatment will be captured.

10.0 CONFIDENTIALITY and PROTECTION of RESEARCH SUBJECTS

All study-related materials will be stored electronically on password-protected DUHS maintained servers. All personnel involved in the conduct and analysis of data from the study will have ethics training in the protection of research subjects.

11.0 PROTOCOL MANAGEMENT and DATA COLLECTION

This study will be conducted in accordance with applicable Federal regulations and radiation therapy standards. Data will be entered in the study specific database within a timely manner.

12.0 RISKS/BENEFIT ASSESSMENT

Radiation therapy is a standard treatment modality for patients with DLBCL. The risks of treatment are expected to be less since a lower dose of RT will be employed. It is possible that 20 Gy is insufficient which may increase the risk of disease recurrence which may necessitate further treatment. With smaller RT doses, it is expected that both acute and long-term toxicity will be less.

13.0 COSTS

Since chemotherapy and radiation therapy are standard of care for DLBCL, all costs of the treatment as well as follow-up examinations will be billed to the patient or their insurance carrier.

14.0 STATISTICAL CONSIDERATIONS

Statistical Analysis of Primary Objective

This trial will accrue 62 patients over a time period of approximately 5-6 years. The primary objective is to determine whether the *observed* 5-year LC rate, estimated from the Kaplan-Meier curve of time-to-local failure, is as high as that observed in historical controls, i.e., 0.90. Time -to-local-failure is defined as time from on-study to time of local failure; deaths are censored; distant failures are ignored (i.e., we will continue to follow for local failure after observing a distant failure). The lower 90% confidence bound of the 5-year LC rate will be calculated, and if the lower 90% bound is ≥ 0.84 , the study will be considered a success. This decision rule is equivalent to requiring that the observed 5-year LC rate be ≥ 0.90 . If the true 5-year LC rate is 0.84 (0.94), there is 7% (87%) probability that the lower bound will be ≥ 0.84 . These probabilities (7% and 87%) are the alpha (one-sided) and power, respectively, for the null hypothesis that the 5-year LC rate is ≤ 0.84 and the alternative hypothesis that the 5-year LC rate is ≥ 0.94 . The expected number of events in this study assuming each of these distributions is 15.0 and 5.4, respectively.

The operating characteristics of the design above take into account two interim analyses designed to stop the study early when there is evidence that the null hypothesis is true. The first analysis will be done after 45 person-years (PY) of follow-up have accumulated (at about year 3). We will also perform a second interim analysis if the trial is accruing slower than anticipated, after 185 person-years of follow-up. These interim analyses will assess whether the cumulative incidence of LC (i.e., the number of events divided by the total PY of follow-up) exceeds the values shown in the table below. If the cumulative incidence is “too high,” the trial will stop. The probabilities of stopping early are also shown in the table.

Stage	Analysis time	Minimum cumulative incidence needed to stop the trial and accept the null	Probability of accepting the null when the null is true (when the alternative is true)
1	~3 years (45 PY)	0.044 (2/45)	0.35 (0.06)
2	~6 years (185 PY)	0.032 (6/185)	0.32 (0.01)
3 (Final)	11 years	NA	0.26 (0.05)

Statistical Analysis of Secondary Objective 1

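### A third confirmed local failure before the first interim look already meets its stopping boundary, yet nothing pauses enrolment until the look: a cheap change with a small gain

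*Combined protocol and SAP*

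**What the plan says.** Section 14.0 (Statistical Analysis of Primary Objective) plans 62 patients: "This trial will accrue 62 patients over a time period of approximately 5-6 years". It schedules two futility looks, the second only if accrual is slow. On the first it says: "The first analysis will be done after 45 person-years (PY) of follow-up have accumulated (at about year 3"). The statistic is local failures divided by total PY of follow-up, and the first boundary is 0.044 (2/45). The stated probability of stopping there is 0.35 under the null (5-year LC 0.84) and 0.06 under the alternative (0.94).

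The direction of the boundary is worded in two ways. The text stops the trial if the ratio "exceeds the values shown in the table below". The table column is headed "Minimum cumulative incidence needed to stop the trial and accept the null". At exactly 45 PY the text needs three failures and the table header needs two.

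Elsewhere, Section 9.2 lists reasons for taking an individual patient off protocol, such as "Non compliance with protocol requirements". Section 9.4 covers adverse event capture. Section 11.0 says of the data: "Data will be entered in the study specific database within a timely manner". Sections 4.0 and 7.0, on recruitment and registration, contain no rule for pausing enrolment. The front matter was not available to us.

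**The concern.** The boundary is read at one time, but its outcome can be known earlier. Once three local failures have occurred, further follow-up before the look can lower the ratio but cannot realistically bring it under 2/45. Enrolment nevertheless continues until the look.

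Section 12.0 names the harm at issue: "It is possible that 20 Gy is insufficient which may increase the risk of disease recurrence which may necessitate further treatment". A patient who enters after the third failure takes that risk in a trial that its own rule will almost surely stop, and that patient's data will hardly ever alter the first-stage decision.

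**Working it through.** **Inputs from Section 14.0.** 62 patients over 5 to 6 years; first look at 45 PY or about year 3; boundary 2/45; LC 0.84 (null) and 0.94 (alternative).

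**Assumptions.** Constant hazard, uniform entry, no deaths. Results come from simulation, 40,000 trials per setting, apart from the closed-form steps shown.

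**1. The plan's own figure.** Hazard = −ln(LC)/5, which is 0.03487 per year (null) and 0.01238 (alternative). Expected failures at 45 PY are 1.569 and 0.557.
- Two failures stop at exactly 45 PY: 1 − e^(−1.569)(1 + 1.569) = 0.465 (null); 0.108 (alternative).
- Three failures needed: 1 − e^(−1.569)(1 + 1.569 + 1.231) = 0.209 (null); 0.019 (alternative).
- Read at calendar year 3, 6-year accrual, stop if failures/PY ≥ 2/45: 0.34 (null); 0.06 (alternative).

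Only the last is close to the stated 0.35 (0.06). We infer that the design was probably computed with a year-3 read. The protocol does not say so, and both reads are carried below.

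**2. When three failures settle the look.** At 45 PY, 3/45 = 0.067, above 0.044 under either wording. Three failures equal the boundary at 3 ÷ (2/45) = 67.5 PY, so they meet it at any read up to 67 PY.

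**3. Where the look falls.** Entry rates are 62/6 = 10.33 and 62/5 = 12.4 per year. Ignoring failures, 45 PY is reached at √(90/10.33) = 2.95 years (about 30 enrolled) or √(90/12.4) = 2.69 years (about 33 enrolled). By year 3, follow-up is about 10.33 × 9/2 = 46.5 PY or 12.4 × 9/2 = 55.8 PY. A year-3 read with 5-year accrual exceeds 67.5 PY in about 4% of null trials.

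**4. Patients entering between the third failure and the look.** Ranges cover both reads.

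| True LC | Accrual | Third failure before look | Per trial, immediate detection | Per trial, 6-month lag |
|---|---|---|---|---|
| 0.84 | 6 years | 21% | 1.2 to 1.3 | 0.4 to 0.5 |
| 0.84 | 5 years | 21% to 29% | 1.4 to 2.1 | 0.5 to 0.8 |
| 0.90 | 6 years | 7% | about 0.4 | about 0.1 |
| 0.94 | 5 to 6 years | 2% to 3% | 0.1 to 0.2 | below 0.1 |

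The first row is 0.21 × 5.6 to 0.21 × 6.2, where 5.6 to 6.2 is the mean number of later entrants when the third failure comes first.

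**5. In local failures.** Suppose patients not enrolled would have LC 0.90, the plan's historical figure, instead of 0.84. With 6-year accrual this avoids 0.06 × 1.2 to 0.06 × 1.3, about 0.07 to 0.08 local failures per trial, or about 0.03 with a 6-month lag.

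**6. Decisions changed.** At a 45-PY read, none. At a year-3 read, PY keep accruing after the third failure, so a few trials that would have continued now stop. With the rule limited to 67 PY, this is about 0.02% of null trials (6-year accrual) or 0.6% (5-year) under uniform entry, and about 0.2% or 1.4% if arrivals are Poisson.

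**The case against.** The strongest reply is that nothing here is wrong. Scheduled futility looks are standard, and Section 14.0 says its operating characteristics allow for them. That stands: this is an optional improvement.

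The gain is also small, and slow detection shrinks it. Section 9.3 says of routine follow-up: "This usually involves a CT or PET/CT every 6 months for 2 years following the completion of radiation treatment". Imaging is left to the treating physicians. With a 6-month lag and 6-year accrual, the median number of patients spared, when the third failure does come first, is zero. That stands too, and it limits how much weight the point can bear.

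A third objection changes the remedy. Whether a relapse is local depends on its position relative to the radiation fields, and Section 9.3 recommends imaging for this without requiring it. About 64% of the affected null trials (6-year accrual) have exactly three failures at the look, so one reclassification could reverse the stop. As an illustration, if 10% of recorded failures were reclassified by year 3, about 11% (6-year) to 18% (5-year) of affected null trials would not have stopped. Closing enrolment outright on unconfirmed failures would therefore be unsafe. The rule should pause, confirm and then decide.

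A reader might also infer that a second failure already settles the look. That follows only from the table header, and only at a read of exactly 45 PY. The text's wording needs a third. Resolving that conflict is a separate matter; the third failure is used here because it meets the boundary under both.

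**Conclusion.** The point holds as a low-priority improvement. The first boundary is read only at about 45 PY, no section available to us pauses enrolment earlier, and a third confirmed local failure before then meets the boundary under either wording. At LC 0.84 an earlier pause spares roughly one to two patients per trial at best and under one with a realistic detection lag. It is worth making because it costs almost nothing.

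Two stronger readings are not supported. One is that the trial lacks protection against an ineffective regimen. It has planned futility looks, and any patients exposed needlessly are few. The other is that the single reading distorts the error rates. At a 45-PY read, adding the rule changes no decision; at a year-3 read, simulated success moves by no more than 0.001 under either hypothesis (uniform entry).

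The sizes rest on constant hazard, no deaths and the stated accrual. The simulation gives success under the null of 0.10 to 0.11 against the plan's 7%, so it does not fully reproduce the later stages, and the figures below 1% are approximate. The first-look figures, on which this point rests, agree closely with the plan at a year-3 read.

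**What to change.** Add to Section 14.0, after the description of the first interim analysis:

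> If a third local failure is recorded before the first interim analysis and before 67 PY of follow-up, enrolment is suspended. Once all three are confirmed as in-field against the radiation treatment fields, the first interim analysis is done at once with the person-years then accrued and, if the boundary is met, the trial stops. If a failure is reclassified, enrolment resumes. Enrolled patients continue in follow-up.

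Existing staff would need to log local failures promptly and confirm them against the treatment fields. Enrolment may pause briefly without a stop following. A trial that stops sooner gives slightly less precise descriptive estimates. If the look would otherwise be read at year 3, the small share of changed decisions in step 6 of the working applies. No new committee or boundary is needed.

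### The first-look stopping probabilities (0.35 and 0.06) and the 87% power reproduce only with an unstated constant failure rate and a look at calendar year 3; the rule as written, triggered at 45 person-years, does not deliver them

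*Combined protocol and SAP*

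**What the plan says.** All of the design text is in Section 14.0, under the primary objective.

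- Size and accrual: "This trial will accrue 62 patients over a time period of approximately 5-6 years".
- Hypotheses: "the null hypothesis that the 5-year LC rate is ≤ 0.84 and the alternative hypothesis that the 5-year LC rate is ≥ 0.94".
- Error rates: "If the true 5-year LC rate is 0.84 (0.94), there is 7% (87%) probability that the lower bound will be ≥ 0.84". The success rule is also given in observed terms: "This decision rule is equivalent to requiring that the observed 5-year LC rate be ≥ 0.90".
- First look: "The first analysis will be done after 45 person-years (PY) of follow-up have accumulated (at about year 3"). The table puts the boundary at 0.044 (2/45), with stopping probabilities of 0.35 under the null and 0.06 under the alternative.
- Second look: 185 person-years, about year 6, boundary 0.032 (6/185), planned if accrual is slow.
- Interim statistic: whether "the cumulative incidence of LC (i.e., the number of events divided by the total PY of follow-up) exceeds the values shown". The table's column heading, by contrast, presents the same values as the smallest that would stop the trial.
- Events: "The expected number of events in this study assuming each of these distributions is 15.0 and 5.4, respectively".

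The section names no failure-time distribution and gives no sensitivity of the boundary to failure timing. The only text bearing on timing is the description of usual imaging in Section 9.3: "This usually involves a CT or PET/CT every 6 months for 2 years following the completion of radiation treatment".

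**The concern.** The interim statistic is a rate, events per person-year, while the hypotheses concern a 5-year proportion. The two correspond one-to-one only if the hazard is flat. At about year 3 some 30 patients have been followed for about 1.5 years on average, so the first look sees almost only the early hazard. A regimen with 5-year LC of 0.94 whose few failures come early would be judged against a boundary calibrated for evenly spread failures.

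The look is also described in two ways, by person-years and by calendar year, and these do not behave alike when the boundary is as small as two events. At stake is the chance of ending a 62-patient trial early on two events when the regimen meets the alternative, and hence whether the stated power is what the rule delivers.

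**Working it through.** **Inputs.** From Section 14.0: 62 patients, 5-year LC 0.84 (null) and 0.94 (alternative), boundaries 2/45 and 6/185, final success if observed 5-year LC is at least 0.90, final analysis at year 11. Assumed: uniform accrual over 6 years, no deaths or dropout, both looks always performed.

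**1. Constant hazards.** λ = −ln(S5)/5, so −ln(0.84)/5 = 0.03487 and −ln(0.94)/5 = 0.01238 per person-year.

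**2. Expected events at year 11.** Follow-up is uniform from 5 to 11 years, so E = 62 × {1 − [exp(−5λ) − exp(−11λ)]/(6λ)}.
- Null: 62 × {1 − (0.8400 − 0.6814)/0.2092} = 15.0, as stated. Only 62 × 0.16 = 9.9 of these fall within 5 years of entry, so about 34% come later. The front-loaded shapes simulated gave fewer (for example 12.2 for a Weibull with shape 0.5), so 15.0 points to a constant hazard.
- Alternative: 5.8, against 5.4 stated. The stated value fits LC of about 0.9445.

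**3. Look at calendar year 3.** Expected follow-up is 62 × 3²/(2 × 6) = 46.5 person-years before time after failure is removed. Simulation with stopping if events/person-years is at least 2/45:

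| Constant hazard | Stage 1 | Stage 2 | Final failure | Success |
|---|---|---|---|---|
| Null, stated | 0.35 | 0.32 | 0.26 | 0.07 |
| Null, simulated | 0.34 | 0.29 | 0.28 | 0.10 |
| Alternative, stated | 0.06 | 0.01 | 0.05 | 0.87 |
| Alternative, simulated | 0.06 | 0.01 | 0.05 | 0.88 |

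The alternative row and the Stage 1 figures reproduce. The stated alpha of 7% does not (about 10%); that is a separate matter.

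**4. Look at 45 person-years, constant hazard.** The event count is close to Poisson with mean μ = 45λ, which is 1.569 (null) or 0.557 (alternative).
- Stop at 2 events: 1 − e^(−μ)(1 + μ) = 0.465 and 0.108. Simulated power is about 0.84.
- Strictly more than 2/45, so 3 events: 0.209 and 0.019.

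Neither pair matches 0.35 and 0.06. The year-3 version lies between them because person-years at year 3 vary: above 45, two events fall short of 2/45 and three are needed.

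**5. Early clustering, LC held at 0.94.** Let p be the share of 5-year failures in years 0-2. Then S2 = 1 − 0.06p, h1 = −ln(S2)/2 and h2 = −ln(0.94/S2)/3. With follow-up spread evenly over 0 to 3 years, 8/9 of person-time lies in years 0-2, so at 45 person-years μ ≈ 40·h1 + 5·h2.
- p = 60%: h1 = 0.0183, h2 = 0.0084, μ = 0.775, P(≥2) = 0.18
- p = 70%: h1 = 0.0215, h2 = 0.0063, μ = 0.890, P(≥2) = 0.22
- p = 80%: h1 = 0.0246, h2 = 0.0042, μ = 1.005, P(≥2) = 0.27

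Simulation of the whole design agrees to about 0.01 (false stop at the first look / power):

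| Share in years 0-2 | Year-3 look, 2/45 | 45-PY look, 2 events | 45-PY look, 3 events |
|---|---|---|---|
| 41% (constant) | 0.06 / 0.88 | 0.11 / 0.84 | 0.02 / 0.91 |
| 60% | 0.11 / 0.84 | 0.19 / 0.78 | 0.05 / 0.88 |
| 70% | 0.14 / 0.81 | 0.22 / 0.74 | 0.06 / 0.87 |
| 80% | 0.17 / 0.79 | 0.27 / 0.70 | 0.08 / 0.86 |

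Like for like, the increase is 0.11/0.06 = 1.8 to 0.17/0.06 = 2.8 for the year-3 look, and 0.19/0.11 = 1.7 to 0.27/0.11 = 2.5 for the 45-person-year look.

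**The case against.** A reader might set 0.27 against the stated 0.06 and infer that early failures make a wrongful stop four or more times as likely. That mixes two bases: 0.06 belongs to the year-3 look and 0.27 to the 45-person-year look, where the constant-hazard value is already 0.11. On the year-3 basis, a four-fold rise needs something close to all failures within two years (0.23-0.24), and nothing in the documents supports so extreme a pattern.

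Nor does Section 9.3 show that failures come early. It describes usual practice, with imaging at the treating physicians' discretion and annual visits continuing after two years. An imaging habit is not a failure-time distribution, so the 60-80% range remains an assumption.

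Clustering also has a favourable side. The existing boundary then stops a truly inadequate regimen more often (year-3 look, null: 0.34 to about 0.67 at an 80% share), and alpha falls slightly rather than rising. The looks exist to stop when the null is true, and Section 12.0 accepts that the reduced dose may be insufficient.

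Finally, the sponsor can say that year 3 was always meant, since the text gives both markers. Then the stated 0.06 and 87% stand under a constant hazard. All of these objections hold. They limit the size of the point, but leave the unstated assumption and the ambiguous trigger in place.

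**Conclusion.** The concern holds in a limited form. The stated first-look probabilities and power depend on a constant hazard and a calendar year-3 look, and the plan states neither as an assumption of the calculation. If the look is triggered by 45 person-years and two events stop the trial, a regimen with LC 0.94 is stopped with probability about 0.11 rather than 0.06, the null is stopped at that look with probability about 0.46 rather than 0.35, and power is about 0.84 rather than 0.87. No early clustering is needed for that.

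Clustering of 60-80% of 5-year failures in years 0-2 would multiply the false stop by about 1.7 to 3 on either basis and lower power to 0.84-0.79 (year 3) or 0.78-0.70 (45 person-years). These figures rest on 6-year uniform accrual, no deaths or dropout, and piecewise-constant hazards. The harm is lost power for an effective regimen, not a higher alpha. The point is worth correcting but is not a fundamental flaw.

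**What to change.** In Section 14.0:

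1. State whether the first look is triggered by calendar time or by 45 person-years.
2. State whether exactly 2/45 stops the trial, so that the text and the table heading agree.
3. Name the failure-time distribution assumed, and restate alpha, power and all stage probabilities for the chosen rule under a constant and a front-loaded distribution (for example 60-80% of 5-year failures in years 0-2).

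The cost is an amendment to one section and a rerun of the design calculation, with no new patients or procedures.

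A boundary of 3/45 is an option for the sponsor to weigh, not a required correction. At a 45-person-year look it holds the false stop at 0.02-0.08 and power at 0.86-0.91 over the range above. The price is real: first-look stopping under the null falls to 0.21-0.53 (under a constant hazard from 0.46 to 0.21, less than half), and alpha rises to about 0.09-0.10, from 0.06-0.09 with two events and against the stated 7%.
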